11.6 Analysis of the Secondary Endpoint(s)

11.6.1 Group 1

We will calculate the proportion of randomized patients that received all implementation components to which they were randomized in the appropriate time frame. We will estimate the confidence interval using the normal approximation to the binomial distribution. We will accept the hypothesis if the two-sided confidence interval (alpha=0.05) for the secondary endpoint excludes 0.66.

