The study is designed as a pilot cluster randomized quality improvement trial. For each patient, a target clinician will be identified, defined as either a cardiologist at Michigan Medicine, if the patient has seen one in the past year, or else the clinician of record on file with the anticoagulation service. For each patient, assignment to one of two clinician-level QI strategies will be done at the cluster level according to the identity of the target clinician. Each clinician (cluster) will be randomized 1:1 to receive either clinician notification (consisting of a notification message sent in the electronic health record) or clinician notification + nurse facilitation (consisting of a similar notification, but which additionally includes provision of clinically relevant information identified on chart review, along with other steps to facilitate appropriate care). Separately, patients will be individually randomized to receive an activation guide that provides patient education and encouragement to discuss medication optimization with their clinicians, or to usual care. Following delivery of the QI strategies, patients, clinicians, and anticoagulation staff will be invited to participate in semi-structured interviews about their experiences with and perceptions of the QI strategies.

Group 1: Primary Objective: To explore the feasibility of patient participation in a one-time assessment of medication use following delivery of the QI strategies.

Group 1: Secondary Objectives: To explore the feasibility of delivering QI strategy components to clinicians and patients as intended.

Group 2: Primary Exploratory Objective: To explore the feasibility and appropriateness of the QI strategies from the perspective of primary care clinicians to inform a future clinic-wide trial.

Endpoints*:

Group 1: Primary Endpoint: The proportion of randomized patients who complete a brief phone assessment (patient assessment #1) at week 5.

Group 1: Secondary Endpoints: The proportion of patients and clinicians who received the QI strategies to which they were randomized.

Group 1: Exploratory Endpoints: Multiple additional quantitative endpoints will be evaluated, as documented in the section 4 of the protocol.

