Group 2: There is no quantitative endpoint. The primary exploratory objective is to conduct a qualitative evaluation of primary care providers' perceptions of the intervention strategies. **Group 2 Exploratory endpoints:** Multiple exploratory endpoints will be evaluated, as documented in section 4.

Phase or Stage: This project is a pilot feasibility quality improvement trial.

Description of Sites/Facilities Enrolling Participants: Participants will be included from a single site (the Michigan Medicine anticoagulation monitoring service in Ann Arbor, Michigan, USA).

Description of Study Intervention/Experimental Manipulation: **Quality improvement implementation strategies to be delivered:** Two clinician-facing QI strategies will be evaluated, both of which are intended to assist the clinician in making an appropriate decision to optimize patients' medications:

1. **Clinician Notification:** A protocol-driven QI strategy in which an anticoagulation clinic nurse sends a templated message to the patient's target clinician that identifies the patient as high risk for upper GI bleeding, summarizes options for medication optimization, and asks that the clinician manage any medication changes.

2. **Clinician Notification +Nurse Facilitation:** A protocol-driven QI strategy in which an anticoagulation clinic nurse sends a templated message to the patient's target clinician, similar to clinician notification, but which also includes clinical information about the patient identified by the nurse during chart review, along with a concise evidence summary relevant to the patient. In addition, once clinicians decide on a medication optimization plan, the nurse will facilitate execution of the plan and communicate recommendations to the patient.

Two patient-facing strategies will be evaluated:

1. **Patient Activation Guide:** A guide to educate patients about their risk for bleeding and activate them to talk with their clinician about medication changes to reduce their bleeding risk.
2. **Usual care:** No additional education or activation strategies outside of usual care will be included.

Assessments Group 1: Semi-structured interviews will be conducted with patients, clinicians, and anticoagulation staff to evaluate perceptions of the QI strategies, as described in the body of the

protocol. Data will also be extracted from the medical record at multiple timepoints.

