To explore the accuracy of the electronic health record's medication list for ascertaining medication changes	
The accuracy, positive predictive value, and negative predictive value of the electronic health record for use of antiplatelet therapy, and for use of PPIs at the time of assessment #3.
 
The accuracy, positive predictive value, and negative predictive value of the electronic health record for "medication optimization" at the time of assessment #3. A patient will be considered to have had medication optimization if they are either no longer using combination antithrombotic therapy or are using a PPI.

To explore the feasibility of complete collection of study data	
The proportion of patients with complete data entry in RedCAP database at study completion
 
Average duration of interviews on medication use/adherence during patient assessment #3 at week 15-17.

To explore the feasibility of delivering the clinician-level QI strategies	
Proportion of patients whose clinician was sent the clinician-level strategy by the anticoagulation clinic staff in the prescribed time period per the clinic protocol. We will also separately calculate this endpoint for the two levels of the clinician QI strategy.

To explore the feasibility of delivering the patient activation tool	
The proportion of patients randomized to receive the activation guide who were sent the guide in the prescribed period of time, as determined by chart review.
 
The proportion of patients randomized to receive the guide who recalled receiving the guide during patient assessment #1 at week 5.
 
The proportion of patients randomized to receive the guide who recalled reviewing the guide in patient assessment #1 at week 5.

OBJECTIVES	ENDPOINTS

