To explore process outcomes associated with the clinician notification + nurse facilitation implementation strategy	
For patients randomized to clinician notification + nurse facilitation:
 
Number of days taken for clinicians to send a response message to anticoagulation staff after first receiving the clinician notification.
 
Proportion of clinicians who documented their plan-of-care for the patient in the response message to the anticoagulation staff.
 
Proportion of patients randomized to clinician notification + nurse facilitation for whom the anticoagulation nurse provided patient education.
 
Proportion of patients randomized to clinician notification + nurse facilitation for whom the anticoagulation nurse pended the PPI order.

To explore aspects of effectiveness of the implementation strategies.	
For anticoagulation clinic patients who meet inclusion criteria but are not randomized to a QI strategy in the pilot trial, whether or not they initiate PPI or discontinue antiplatelet therapy over the study period, as determined using electronic health record data, which will provide data on use of the evidence-based practices in usual care.
 
For randomized patients, initiation of either a PPI or discontinuation of all antiplatelet therapy at week 5 (patient assessment #1), and at week 15-17 (patient assessment #3), as determined by patient interview.
 
For randomized patients, the level of adherence to the recommended medication change (either PPI initiation or antiplatelet discontinuation) at week 15-17 measured using the Wilson questionnaire, as determined by patient assessment #3.
 
Documentation of a recommendation by one of the patient's Michigan Medicine clinicians to discontinue antiplatelet therapy or initiate a PPI as indicated by a clinical documentation or by a change in the EHR medication list, ascertained by EHR review.

To explore the appropriateness of antiplatelet therapy used by patients at the time of study randomization.	The clinical appropriateness of antiplatelet therapy at the time of study initiation, classified as either (probably guideline concordant, probably not guideline concordant, or uncertain), based on detailed chart review and in reference to practice recommendations (Appendix 1).

OBJECTIVES	ENDPOINTS

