5 STUDY DESIGN

5.1 Overall Design

This is a pragmatic, single center, feasibility pilot of a cluster randomized quality improvement trial with embedded individual randomization to evaluate implementation strategies to increase the use of evidence-based practices (EBPs) to reduce bleeding in patients who are using combination antithrombotic therapy and who are managed by the Michigan Medicine anticoagulation monitoring service. Two clinician-level strategies will be evaluated: (1) a clinician notification that identifies the patient as high-risk for upper GI bleeding and suggests discontinuing the antiplatelet agent or initiating a PPI; and (2) a clinician notification + nurse facilitation strategy in which a nurse undertakes multiple steps in an effort to overcome barriers to medication optimization. In addition, two patient-level strategies will be evaluated: (1) a patient activation tool; and (2) usual care. Clinicians will be cluster randomized, such that all the patients cared for by a single clinician will receive the same clinician-level notification.

Simultaneously, patients will be individually randomized to one of the two patient-level strategies.

Since this is a pilot study to assess feasibility of delivering all QI implementation strategies and acceptability of the strategies, the study design may be modified during the study period if problems are identified. Any study design modifications will be submitted to the IRB at Michigan Medicine as study amendments and documented in the amendment section on page 6 of this document.

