7 STUDY QUALITY IMPROVEMENT STRATEGIES

7.1 Study Implementation Strategy Administration

7.1.1 Quality Improvement Strategy Descriptions

All of the implementation strategies have been documented into clinical protocols approved by the anticoagulation clinic to address upper GI bleeding risk. All study QI strategies will be delivered by anticoagulation clinic staff as part of routine care.

Two clinician-facing implementation strategies will be evaluated.

1. **Clinician Notification:** An anticoagulation clinic nurse sends a templated message to the patient's target clinician that points out the patient's high risk for upper GI bleeding, summarizes guidelines on appropriate antiplatelet drug use and PPI gastroprotection, and recommends that the clinician consider either discontinuing the patient's antiplatelet drug or initiating a PPI for gastroprotection.
2. **Clinician Notification + Nurse facilitation:** An anticoagulation clinic nurse sends a templated message to the target clinician, similar to the clinician notification strategy. However, the message also includes clinical details about the patient's indication for antiplatelet therapy, ascertained by the nurse during chart review, and is intended to streamline decision-making by the clinician. In addition, the nurse will pend orders for medication changes if given instructions by the clinician and will communicate any recommendations to the patient on the clinician's behalf.

In addition, two patient-facing implementation strategies will be evaluated:

1. **Patient Activation:** A written guide to educate patients about their risk for bleeding and encouraging patients to talk with their clinician about medication changes to reduce their bleeding risk. This will be sent to patients through their preferred mode of communication (mail or patient portal). All patients will only be sent the guide once.
2. **Usual care:** With usual care, the anticoagulation clinic will not send the patient activation guide or other project-specific materials to the patient.

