7.3 Measures to Minimize Bias: Randomization and Blinding

Assignment to one of two clinician-level QI strategies will be done at the cluster level according to the identity of the clinician to be contacted. The cluster of patients cared for by each anticoagulation clinic target clinician will be randomized 1:1 to get either clinician notification (CN) or clinician notification + nurse facilitation (CN+NF). Patients will also be individually randomized to receive the patient activation guide or to a usual care arm.

Neither patients nor clinicians can practically be blinded.

As this is a pragmatic, quality improvement trial, there is no intention to blind anticoagulation clinic staff or research team members to group assignment.

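### Section 11.6.1: the Wald rule for concluding that more than 66% of strategies were delivered accepts too easily at these sample sizes, and any within-clinician correlation would add to the error (low severity; ICC unknown)

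*Combined protocol and SAP*

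**What the plan says.** Section 11.6.1 takes the share of randomised patients who got every assigned component on time, puts a normal-approximation binomial interval around it, and then decides: "We will accept the hypothesis if the two-sided confidence interval (alpha=0.05) for the secondary endpoint excludes 0.66". Section 11.4.1 supplies the hypothesis, that delivery is above 66%.

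Sections 6.1.1 and 6.4.1 set Group 1 at 40–51 patients of 12 clinicians. The clinicians are drawn at random, six cardiologists and six non-cardiologists, and every eligible patient of each is taken. The clinician is also the unit of randomisation. Section 5.1: "Clinicians will be cluster randomized, such that all the patients cared for by a single clinician will receive the same clinician-level notification". Section 7.3: "The cluster of patients cared for by each anticoagulation clinic target clinician will be randomized 1:1".

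Nothing in sections 11.1 to 11.11 mentions an ICC, a design effect, a cluster-adjusted variance or a mixed model. The only precision figure is in section 11.1.1, for the primary endpoint: 80% to within 13 points with n=40.

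Section 7.1.1 has clinic staff deliver all strategies. In the nurse-facilitation arm some steps wait on the clinician: "once clinicians decide on a medication optimization plan, the nurse will facilitate execution of the plan and communicate recommendations to the patient" (Synopsis) and "the nurse will pend orders for medication changes if given instructions by the clinician" (section 7.1.1).

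**The concern.** The interval in section 11.6.1 decides a stated hypothesis, so its error rate matters. Two features push that error above nominal. The first is certain: the Wald interval is inaccurate for a proportion near 0.8 with 40–51 observations, and its lower limit sits too high. The second is conditional: the interval treats patients as independent although they come as whole clinician clusters, so a positive within-clinician correlation makes it too narrow.

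At stake is whether the pilot reports that delivery exceeded 66% more readily than the stated alpha implies, when that conclusion is meant to inform a clinic-wide trial.

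**Working it through.** **Inputs from the documents.** Benchmark 0.66 and two-sided alpha 0.05 (sections 11.4.1, 11.6.1); n = 40 to 51 and 12 clinicians (section 6.1.1). Because the hypothesis is that the rate exceeds 66%, I read the rule as lower limit above 0.66, which has a nominal error of 2.5%.

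**Assumed, because the documents give no value.** The ICC, and the cluster sizes. Near-equal: 8×3 + 4×4 (n=40), 9×4 + 3×5 (n=51). Unequal: 1,1,1,2,2,2,3,3,4,5,6,10 (n=40) and 1,1,2,2,3,3,4,4,5,6,8,12 (n=51).

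**The plan's own figure.** 1.96 × √(0.8 × 0.2 / 40) = 12.4 points, which agrees with section 11.1.1.

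**Wald cut-offs.** Lower limit = p − 1.96√(p(1−p)/n).
- n=40: 31 gives 64.6%; 32 gives 0.800 − 0.124 = 67.6%. Accept at 32 or more.
- n=51: 39 gives 64.8%; 40 gives 67.1%. Accept at 40 or more.

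**Error with independent patients.** Exact binomial at p = 0.66: P(X ≥ 32 of 40) = 4.0%; P(X ≥ 40 of 51) = 3.9%.

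**Wilson cut-offs.** Lower limit = [p + z²/2n − z√(p(1−p)/n + z²/4n²)] / (1 + z²/n).
- 32/40: (0.8480 − 0.1329)/1.0960 = 65.2%, not accepted. 33/40: (0.8730 − 0.1272)/1.0960 = 68.1%, accepted.
- 40/51 gives 65.4%; 41/51 gives 67.5%. Accept at 41 or more.
- P(X ≥ 33 of 40) = 1.7%; P(X ≥ 41 of 51) = 1.8%.

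So the planned and Wilson rules differ by one patient.

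**Adding within-clinician correlation.** Each correlated cluster was given a beta-binomial count with mean 0.66. Totals came from exact convolution (all 12 clusters) or 200,000 simulated trials (a random six; the clustered interval). The clustered interval uses SE = √[(12/11) Σ(xⱼ − mⱼp)²]/n and t on 11 df. Each range below covers both sample sizes and both sets of cluster sizes, and simulated values carry about 0.2 points of noise.

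| Chance of acceptance at a true 66% | Planned Wald | Wilson | Clustered t |
|---|---|---|---|
| ICC 0 | 3.9–4.0% | 1.7–1.8% | 3.3–4.1% |
| ICC 0.10, six clusters | 4.8–5.9% | 2.2–3.2% | 3.5–4.6% |
| ICC 0.10, all twelve | 5.8–7.8% | 2.9–4.7% | 3.9–5.2% |
| ICC 0.30, all twelve | 9.4–14.7% | 5.5–10.4% | 4.6–7.0% |

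**Effect at the planned cut-offs.** The design effect is 1 + (m − 1) × ICC, where m is the size-weighted mean cluster size: 3.40 or 5.25 for n=40, 4.29 or 6.45 for n=51. At ICC 0.10 it is 1.24 / 1.43 and 1.33 / 1.55 (near-equal / unequal). The lower limit at 32/40 moves from 67.6% to 66.2% / 65.2%, and at 40/51 from 67.1% to 65.4% / 64.4%.

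**The case against.** The strongest objection is that the target clinician barely influences the outcome. Clinic nurses send every message and guide, the guide is randomised individually, and patients enter in weekly batches. Correlation by nurse or entry week is at least as plausible, and adjusting by clinician does not address it.

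The one documented route to within-clinician correlation is the facilitation steps that await a clinician's decision, in about six clusters, and those may not count. Section 4.1 scores clinician-level delivery as "Proportion of patients whose clinician was sent the clinician-level strategy by the anticoagulation clinic staff in the prescribed time period" and lists the later steps separately as exploratory, for example "Proportion of patients randomized to clinician notification + nurse facilitation for whom the anticoagulation nurse pended the PPI order". Section 11.6.1 does not say which steps are components. It counts patients only, while the Synopsis words the endpoint as "The proportion of patients and clinicians who received the QI strategies to which they were randomized".

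A clustered interval from 12 clusters is also unstable. In simulation at ICC 0 and a true 66% it came out narrower than the planned interval in about 29–41% of trials.

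All of this stands, and it is why clustering is the secondary part of the point. It does not touch the excess at ICC 0, which needs no assumption about clinicians. Nor does it show the ICC to be zero: clinicians were sampled as whole clusters and the result is meant to carry beyond these twelve.

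**Conclusion.** The sure error is the Wald interval: 4.0% (n=40) or 3.9% (n=51) against 2.5%. Clustering can only be stated conditionally. At ICC 0.10 it takes the error to about 4.8–5.9% (six correlated clusters) or 5.8–7.8% (all twelve). If the ICC is near zero it adds almost nothing. The ICC values and cluster sizes are assumptions, and n=40 and n=51 are the two ends of the target range.

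A reader might infer that, because clinicians are randomised as clusters, the delivery conclusion is invalid or its error is 10% or more. The documents do not support that. They give no ICC, clinic staff perform the delivery, no between-arm test is planned, and the double-digit figures need an ICC near 0.30 in all or nearly all clusters, for which no mechanism is described.

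Nor is clustering shown to be a fault of the primary endpoint or sample size. Section 11.5.1 uses the same interval and benchmark, so the ICC 0 arithmetic carries over, but nothing in the documents ties completion of a phone call to the target clinician.

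The undefined list of components and the unit of count are missing detail. Severity is low: a secondary feasibility endpoint in a pilot, with the point estimate unaffected.

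**What to change.** Amend section 11.6.1 only; no new data are needed.

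1. Base the 66% rule on the lower limit of a two-sided 95% Wilson interval (33/40 or 41/51). Naming the lower limit also closes a wording gap: read literally, excluding 0.66 is also met by 20/40 or fewer, or 26/51 or fewer.
2. Report beside it a clinician-clustered t interval. Its degrees of freedom should reflect the clinicians who contribute patients and the cardiologist/non-cardiologist strata (12 − 2 = 10 if all contribute). The simulated figures above use 11 df without strata, so they are approximate for this version.
3. If the Wilson rule accepts but the clustered interval includes 0.66, describe the acceptance as not robust to clustering.

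**Why Wilson leads.** It brings the error below 2.5% at ICC 0. At ICC 0.10 it gives 2.2–3.2% (six clusters) or 2.9–4.7% (all twelve), against 3.5–4.6% and 3.9–5.2% for the clustered interval alone. At ICC 0.30 in all twelve the order reverses, which is the reason to show both.

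**Cost.** At a true 80% and ICC 0, acceptance falls from 59% to 44% (n=40) and from 69% to 56% (n=51). The clustered interval used alone would cost about 4–8 points at ICC 0 and 11–15 points at ICC 0.10 in all twelve clusters. Neither interval covers correlation by nurse or entry week.

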11.7 Exploratory Analyses

11.7.1 Group 1

Exploratory analyses will mainly consist of descriptive analyses using cross-tabulations, means, standard deviations and proportions. The accuracy, positive predictive value, and negative predictive value will be calculated for antiplatelet use, PPI use, and “medication optimization” at multiple time points, comparing the EHR medication list to self-report (reference standard).

11.7.2 Group 2

Exploratory analyses will mainly consist of descriptive analyses using cross-tabulations, means, standard deviations and proportions.

11.8 Other Analyses

N/A

11.9 Safety Analyses

N/A

11.10 Planned Interim Analyses

None planned.

11.11 Subgroup Analyses

N/A

12 SUPPORTING DOCUMENTATION AND OPERATIONAL CONSIDERATIONS

12.1 Regulatory, Ethical, and Study Oversight Considerations

12.1.1 Informed Consent Process

12.1.1.1 Quality improvement strategy delivery (Both Group 1 and Group 2)

The types of quality improvement strategies (clinician notifications and patient educational handouts) described in this document are routinely used by the anticoagulation clinic as part of clinical care to improve the safety of patients using warfarin. The quality improvement strategies used in this pilot trial were developed specifically for use as part of a quality improvement effort to promote the use of evidence-based practices and reduce bleeding risk among the anticoagulation clinic's patient population.

We request a waiver of informed consent for delivery of the quality improvement strategies. This is justified on the grounds that the study presents only minimal risk to participants (and is likely to be beneficial), the waiver does not adversely affect the rights and welfare of participants, and the research could not practically be carried out without the waiver. The study could not practically be carried out if patients and clinicians are consented because the intent of the pilot quality improvement trial is to evaluate the feasibility of a large scale quality improvement project, which would not include informed consent, i.e., if patients were consented, the pilot would diminish the validity of the results.

